A Multi-center Evaluation of the NEMO™ Gauge to Aid in Correct Positioning of the Endotracheal Tube after Intubation of Critically Ill Patients

STUDY PROTOCOL

Revision 1

Study Lead Investigator: [name] MD, MS, Division of Pulmonary and Critical Care Medicine, Loma Linda University, California

Loma Linda University

Medical Center

Site Principal Investigator:

[name][¶]

Loma Linda Veterans Affairs

Medical Center

Site Principal Investigator:

[name][§]

Riverside University Medical

Center

Site Principal Investigator:

[name][^]

[¶]Division of Pulmonary and Critical Care Medicine, Department of Medicine, Loma Linda University, Loma Linda, CA.

[§]Medical Service, Pulmonary and Critical Care Section, VA Loma Linda Healthcare System, Loma Linda, CA.

[^]Department of Pulmonary and Critical Care Medicine, Riverside University Medical Center, Moreno Valley, CA.

Background and Significance:

Endotracheal tube (ETT) malposition is associated with high incidence of adverse outcomes such as severe atelectasis, pneumothorax, refractory hypoxemia, and even death¹. The rate of ETT malposition among experienced clinicians in the literature is reported to be between 9 and 16%²⁻⁵.

In the setting of emergent intervention that determines life altering outcomes, physicians often rely on point of care devices and modalities to guide their management plans. Currently, chest radiographs are utilized to assess for ETT position after intubation⁶. The median cost of a chest radiograph typically ranges between \$100 and \$500⁷. The average time between the request for a chest radiograph and visual evaluation of the study by a radiologist or experienced clinician is rarely less than one hour. Novel and cost-effective technology is needed to rapidly aid in confirming ETT position immediately after a critically ill patient is intubated.

Device Overview:

The NEMO™ Gauge (Ciel Medical, San Carlos, CA) is an ETT positioning *bougie* that has color-coded depth markers to help the user determine and confirm the position and depth of the tip of the ETT. The NEMO™ Gauge is commercially available in the USA and falls under the FDA regulation Section 868.5790 Tracheal tube stylet, and Classification Product Code BSR (Figure 1).

[figure not shown]

Figure 1: Overview of the NEMO™ Gauge

When the deployment cap (A) is engaged, the expandable tip (E) is advanced out of the catheter providing a bumper to engage with the carina in the patient's airway.

[figure not shown]
[figure not shown]

Figure 2: Deployed expandable tip

[figure not shown]
The expandable tip of the NEMO™ Gauge is made of formed spring wires that are covered with a Pebax sleeve (Figure 2). Pebax is the trade name for a Nylon plastic commonly used in medical devices. The ends of the expandable tip are rounded to present a smooth, round surface on contact with the trachea wall.

The manufacturer's instructions for use include:

[figure not shown]
1. The user removes the positioning clip from the device handle and aligns it on the ETT between the marked distances:

2. The user inserts the NEMO™ Gauge into the ETT until the WHITE measurement marker on the NEMO™ Gauge is visible in the positioning clip window. This indicates that the distal end of the NEMO™ Gauge is aligned with the tip of the ETT.
3. The user expands the distal tip by advancing the deployment cap and continues to advance the NEMO™ Gauge until resistance is felt, and the expandable tip has reached the carina.

4. Once resistance is felt, the user refers to the color of the measurement marker on the NEMO™ Gauge that is present in the positioning clip window. If the window is completely filled by the GREEN measurement marker, the ETT is safely positioned and the NEMO™ Gauge may be removed.
5. If the YELLOW measurement marker on the NEMO™ Gauge is present in the positioning clip window, the ETT position should be adjusted until the GREEN marker is present as shown in the figure below:

Previous Device Testing:

Prior testing of the device by the manufacturer has focused on two main areas:

- Evaluating efficacy of the device in human cadavers
- Evaluating safety of the device in bench models and live porcine models.

Efficacy

Cadaver testing during development of the NEMO™ Gauge has been completed on seven adult cadaver specimens, four male and three female cadavers. All cadaver specimens were fresh (i.e. not embalmed) and were provided by the Stanford University Anatomy Department. At no point during development was any visible damage observed on the tracheal wall or carina of these cadavers.

During a June 2014 cadaver lab, eight Stanford Hospital respiratory therapists were asked to evaluate the feasibility and ease of use of the NEMO™ Gauge. All therapists were provided with a brief in-service training on the use of the device and then asked to confirm ETT position in a cadaveric model. The results were as follows:

- All eight were successful in placing the ETT 2-5 cm above the carina (confirmed by rigid bronchoscopy).
- Of the participants that completed a survey following use (5/8 participants), all of them stated that the tactile feedback during use of the device was adequate and/or that it was clear when they reached the carina.
- On a scale of 1-5, all survey respondents rated the ease of use of the device as a “2 - easy”. (1-very easy, 2-easy, 3-neutral, 4-somewhat difficult, 5-difficult).

Testing in human cadavers has shown the device to be effective at confirming the ETT location as 2-5 cm above the carina.

Safety

The NEMO™ Gauge has been used in a live porcine model to evaluate the risk for mucosal damage during use of the device. A 66-kg pig was intubated with a size 8 ETT. Due to the long length of the porcine airway, the NEMO™ Gauge was not used to position the ETT 2-5 cm above the carina (as expected in humans), but the device was advanced approximately 10 cm through the airway until it engaged with the carina (Figure 3).

[figure not shown]

Figure 3: Chest x-ray taken of the porcine model showing the NEMO™ Gauge (blue arrow) expanded within the porcine airway.

Images were taken before and after use of the NEMO™ Gauge device with a fiberoptic bronchoscope to evaluate mucosal damage (Figure 4 and 5). There was no visible bleeding seen with bronchoscopy.

[figure not shown]

Figure 4: Bronchoscopy images taken before use of the NEMO™ Gauge.

[figure not shown]

Figure 5: Bronchoscopy images taken after repeated (4x) use of the NEMO™ Gauge.

A second, bench model was used to characterize the forces exerted on the tracheal wall by the NEMO™ Gauge during use. The device was inserted into an acrylic 18 mm tracheal model and a 1 mm thick, 1 cm wide, and 6 cm long pressure sensor (TactArray Pressure Sensor, PPS, Los Angeles, CA) was placed on the tracheal internal surface. The maximum pressure exerted by the device was acquired using dedicated software (PPS Camelon TVR Software, PPS, Los Angeles, CA). The average maximum pressure recorded during advancement of the NEMO™ Gauge was 0.54 psi (0.82 psi max). The average maximum pressure recorded during adjustment of the ETT depth in the simulated trachea was 1.78 psi (2.80psi max). Thus, the

forces exerted during advancement of the NEMO™ Gauge are significantly less than the forces exerted during routine adjustment of the ETT.

The above testing suggests that the NEMO™ Gauge is safe for human use. An IRB approved trial is currently underway at a U.S. academic medical center (per Ciel Medical, the manufacturer). This prospective trial studies the use of the NEMO™ Gauge in up to 50 intubated patients undergoing bronchoscopy. Main outcomes include confirmation of accurate measurement of the ETT tip-to-carina distance using the NEMO™ Gauge compared to bronchoscopy measurement, and assessment of mucosal damage during the use of the NEMO™ Gauge. In this study, a bronchoscopy was performed after the use of the NEMO™ Gauge. An interim analysis of 17 patients showed 94% accurate measurement using NEMO™ Gauge (2-5cm from the carina). In one patient (6%) the ETT tip was determined to be inside the 2-5 cm range using the NEMO™ Gauge but was actually at 5.5cm. Eight (8) patients displayed signs of mild mucosal irritation and nine (9) patients showed no irritation after use of the device. No adverse events have been reported to date (ongoing study, unpublished results provided by Ciel Medical).

Specific Aims:

The aim of this study is to investigate the NEMO™ Gauge's ability to accurately and safely determine ETT position, and if needed, guide repositioning of the ETT into the correct position, compared with standard chest radiography.

Inclusion Criteria:

1. Adult patients \geq 18 years of age admitted to the intensive care unit (ICU)
2. Patients who have been intubated or at high risk of being intubated, requiring confirmation of ETT position after intubation as determined by the clinical team
3. Endotracheal tube size 7.0 mm to 8.5 mm in diameter

Exclusion Criteria:

1. Patients with active hemoptysis
2. Patients with known tracheal or bronchial masses prior to endotracheal intubation
3. Patients with known tracheal or bronchial abnormalities requiring surgical repair

4. Patients with ongoing hypoxemia (defined as $\text{SaO}_2 < 85\%$) after endotracheal intubation
5. Any individual involuntarily confined or detained in a penal institution

Study Procedure:

Study physicians will be trained on the use of the NEMO™ Gauge device by viewing a video tutorial, reading the manufacture instructions provided with the device, and performing an ETT position confirmation with the NEMO™ Gauge on a trachea simulation model (mannequin).

[figure not shown]
Patients who are intubated and meet enrollment criteria will be selected for the study procedure (Figure 6). After intubation, the patient will be positioned for the chest radiograph by standard practice. Prior to obtaining the chest radiograph, the NEMO™ Gauge will be used to determine proper tube positioning and should it be necessary the ET tube will be repositioned as per the NEMO™ Gauge's manufacture instructions. Additionally, the operator will auscultate the patient's lung for bilateral breath sounds.

Immediately after use of the NEMO™ Gauge and confirmation of bilateral breath sounds, a chest radiograph will be completed. The distance from the tip of the ET tube to the carina will be measured on the radiograph and will be recorded. Based on current clinical practice⁸⁻⁹, the ET tube will be considered a malposition if it is located less than 2 cm from the main carina, more than 5 cm from the main carina, in the right main stem bronchus, or in the left main stem bronchus.

If the ET tube is considered in a malposition as determined by the chest radiograph, it will be re-adjusted as per standard practice, now without the NEMO™ Gauge. The distance that the ET tube is adjusted will be recorded.

Demographics, diagnostic data, ventilator settings, and ongoing treatments will be recorded. The reason for intubation, ETT size, ETT position, and ETT adjustments will also be recorded. Any complication as a result of the intubation, ETT positioning, and/or NEMO™ Gauge will be recorded.

Figure 6: An outline of the Study Procedure

Primary Outcome:

The percentage of correct ETT position as confirmed by chest radiographs after using the NEMO™ Gauge.

Sample Size / Number of Subjects:

Based on our literature review, correct ETT position after intubation are observed in approximately 91% of patients when verified by standard chest radiograph (the null hypothesis). We hypothesize that use of the NEMO™ Gauge to detect ETT position and make necessary adjustments will result in 98% correct ETT position.

Using a one-sided binomial test, a sample size of 68 patients will detect an increase in ETT correct position of 7% with the use of the NEMO™ Gauge, having a power of 0.84 and a significance level of 0.0492.

Statistical Analysis:

Simple descriptive analysis will be performed, including the percentage of correct ETT position and any complication after the use of the NEMO™ Gauge. See also Interim Analysis below.

Study Duration:

The duration of study enrollment will be 6 months with expected enrollment of approximately 1 patient per week at each participating institution (1 patient x 3 sites x 4 weeks x 6 months ~ 72 patients). We plan to terminate the study after 68 evaluable patients with complete data are enrolled, per the above sample size calculation. Enrollment is planned to start on June 1st, 2016. An interim analysis will be performed at one-half enrollment.

Data Collection:

The investigators at each respective site will collect all data on a standardized case report form. See next paragraph for a listing of the specific data to be collected. All study records, including those which could provide identification, will be kept in a locked file cabinet in a locked office. All electronic records will be kept on a password protected network drive at the

respective sites. Only non-personally identifiable information will be shared with Loma Linda University for data analysis purposes.

Data share agreement between a study site and Loma Linda University must be completed before any data is transferred from the site to Loma Linda University Medical Center (LLUMC). Each study site will submit subject case report forms to the study lead investigator (SLI) for entry into a common database stored at LLUMC. The database is stored on a password protected computer network drive, accessible in the SLI's locked office and research laboratory at LLUMC. Data are de-identified with no PHI.

[figure not shown]
Data Collected:

The following data variables will be collected for every subject: Date of enrollment (consent), name of individual obtaining consent, date of use of the NEMO™ device, name of physician investigator who used the device, patient identifiers, age, height, weight, medical comorbidities, presence/absence of bilateral breath sounds following intubation, endotracheal tube (ETT) size and positioning measurements, record of ETT position changes after use of NEMO™ Gauge, duration of time for the use of the NEMO™ Gauge, time of ordering chest radiograph (CXR), time CXR performed, CXR findings and recording of distance from distal ETT to the main carina, documentation of any additional re-position of the ETT, complications (if any) with intubation and/or use of the NEMO™ Gauge, investigator assessment of whether any complications were related to use of the NEMO™ Gauge.

Human Subjects/Consent:

The enrollment criteria for this study consist of patients requiring or at high risk for requiring intubation and placement on invasive mechanical ventilation. These patients may have altered sensorium and may not be able to provide written informed consent at the time of meeting study enrollment criteria. In such case informed consent may be obtained from a legal authorized representative (LAR).

Patients admitted to the ICU service (irrespective of physical location in the hospital) or their LAR will be presented information about this study and given an opportunity to participate after all their questions have been answered. No study procedures will occur prior to their written informed consent. The consent process is as follows in the figure:

Since it is impossible to know in advance which patients will require intubation and mechanical ventilation in the ICU, we will obtain prospective written informed consent shortly after ICU admission in all patients who may or may not yet require intubation. Not all ICU admitted patients will require intubation during their ICU stay. Thus, we anticipate that only a portion of consented patients may ultimately have study procedures performed on them.

Potential Risks:

Endotracheal intubation is associated with a significant number of adverse events, some of which are serious. These events related to intubation are relatively common and have been studied extensively. Our study is NOT examining the intubation itself, but rather the correct adjustment (if any) of the endotracheal tube AFTER intubation has already occurred. With this in mind, one of the study investigators, not directly involved in the patient care or study procedures will make a determination whether or not events surrounding the intubation are related to intubation vs. to the NEMO™ Gauge.

Nearly all intubated patients undergo suctioning of airway secretions right after intubation and on a regular, as needed basis, multiple times each day for as long as they remain intubated. Suction catheters frequently cause irritation and occasionally bleeding from the tracheal mucosa. The risks associated with the use of the NEMO™ Gauge are approximately similar to the risks associated with routine endotracheal suctioning.

There are always unforeseen risks beyond those of routine endotracheal suctioning; however, we believe the incremental risks from use of this device are minimal. This is based on the pre-clinical device testing (described above) that has occurred as well as to the clinical experience with the device since it has been on the market. The major potential risk associated with this device is the possibility of minor tracheal damage from contact with the tracheal wall. There is a theoretical possibility that the forces exerted on the tracheal wall may cause local mucosal damage during use. The manufacturer has conducted technical performance testing in both live porcine models and bench models to show similar exertion forces as other commercially available products, with favorable results. However, if signs of tissue damage are apparent during use, the NEMO™ Gauge will be removed and the investigators will evaluate the severity of the adverse event and, as needed, will initiate immediate corrective measures. The investigators will determine if any adverse event is attributed to the NEMO™ device. Any serious and/or unexpected adverse device events will be reported to the IRB at the respective site and appropriate federal agencies per their requirements (see Data Safety Monitoring below).

Plan for Communication among IRB:

Any serious adverse events (SAE) associated with this trial will be reported to the local institution IRB immediately in accordance with local reporting regulations. Other non-serious adverse events will be recorded in the local study records and reported to the IRB at the time of continuing review.

Data safety monitoring:

We will follow the FDA guidance, “Medical Device Reporting for User Facilities”: (<http://www.fda.gov/downloads/MedicalDevices/DeviceRegulationandGuidance/GuidanceDocuments/UCM095266.pdf>).

Table 1 - Summary of MDR Reporting Requirements

REPORTER	REPORT WHAT?	TO WHOM?	WHEN?
User Facility	Deaths	FDA and Manufacturer	Within 10 work days
	Serious injuries*	Manufacturer FDA only if manufacturer unknown	Within 10 work days
	Semiannual report of deaths and serious injuries	FDA	January 1 and July 1

*Serious injuries – an injury or illness that is 1) life threatening; 2) results in permanent impairment of a body function or permanent damage to a body structure; or 3) necessitates medical or surgical intervention to preclude permanent damage or impairment.

All deaths and serious injuries at a study site that are determined to be caused by or contributed by the NEMO™ Gauge shall be reported by the site PI, following the site’s institutional process for medical device reporting to the FDA; i.e. the same process used for any FDA-approved medical device. The timeline for reporting should follow the FDA requirements as in Table 1 above.

In addition to the required FDA reporting, the site PI will also submit the report (FDA Form 3500A) to the study lead investigator (SLI) within 72 hours of the event. The SLI will then notify all study sites and the IRB at Loma Linda University of such event.

If the site PI did not voluntarily report the event to MedWatch, the SLI will report such event to MedWatch:

<https://www.accessdata.fda.gov/scripts/medwatch/index.cfm?action=reporting.home>. Such voluntary reporting to MedWatch will potentially be beneficial to society regarding the risk of the NEMO gauge device.

The SLI will also report other deaths or serious injuries to the FDA, MedWatch, and the IRB at Loma Linda University that have not been reported by the individual sites.

Interim Analysis:

A Data Safety Monitoring Board (DSMB) will be organized to provide oversight of the study. The DSMB will consist of two (2) independent intensivists and one (1) biomedical ethicist

unrelated to the study. [name], PhD, Vice-President for Mission and Culture at Loma Linda University, will be invited as our ethicist on the DSMB.

The SLI will organize a mid-study interim analysis at one-half enrollment (34 out of total 68 subjects). Data will be analyzed by the study team (including the SLI, site PI's, and statistician). Results of the analysis will include the percentage of correct endotracheal tube position and any adverse events (including serious injuries and deaths) from the use of the NEMO™ Gauge.

The results of the mid-study analysis will be submitted to the DSMB for review. Depending on the number and severity of adverse events, the SLI and DSMB will determine whether enrollment at all study sites should cease.

The SLI will also perform an event related interim analysis throughout the study period if a death or serious injury is determined to be caused by or contributed by the NEMO gauge. The event will be reported to the IRB at Loma Linda University. In such situation, the SLI and DSMB will determine whether enrollment at all study sites should cease until a complete review of the event is completed.

References:

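### The trial is sized on a one-sided binomial test of 91% against 98%, but no section commits to running that test, or reporting any interval, on the final data

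*Combined protocol and SAP*

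**What the plan says.** The primary outcome is "The percentage of correct ETT position as confirmed by chest radiographs after using the NEMO™ Gauge", so each patient contributes a yes or a no.

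The Sample Size / Number of Subjects section sets up a formal hypothesis test:

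- Null: "correct ETT position after intubation are observed in approximately 91% of patients when verified by standard chest radiograph (the null hypothesis").
- Alternative: "We hypothesize that use of the NEMO™ Gauge to detect ETT position and make necessary adjustments will result in 98% correct ETT position".
- Test and size: "Using a one-sided binomial test, a sample size of 68 patients will detect an increase in ETT correct position of 7" percentage points, "having a power of 0.84 and a significance level of 0.0492".

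The Statistical Analysis section comes next. Its whole content is "Simple descriptive analysis will be performed, including the percentage of correct ETT position and any complication after the use of the NEMO™ Gauge", followed by a pointer to Interim Analysis.

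The Interim Analysis section, for the look at 34 of 68 patients, says "Results of the analysis will include the percentage of correct endotracheal tube position and any adverse events". It names no test and bases the decision on stopping enrolment on adverse events.

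Study Duration uses the calculation only to end enrolment: "We plan to terminate the study after 68 evaluable patients with complete data are enrolled, per the above sample size calculation".

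**The concern.** The comparison with 91% is the only one in the documents that carries a stated hypothesis, and enrolment ends on the calculation built for it. Yet the section that defines the analysis calls it descriptive, and its one cross-reference adds no inference. An analyst could follow Statistical Analysis to the letter, report a percentage, and never run the test.

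A percentage alone cannot separate a result that exceeds 91% by chance from one that rejects 91% at the planned level. The design is single-arm against a fixed external figure, and the study team, including the lead investigator, sees the percentage at half enrolment. Without a rule written in advance, what counts as success could be settled after the data are known. The stated alpha and power describe the conclusion only if the test is actually the basis for it.

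**Working it through.** **Inputs**, all from Sample Size / Number of Subjects: n = 68, p0 = 0.91, p1 = 0.98, one-sided binomial test, stated power 0.84, stated significance level 0.0492.

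**Step 1. Reproduce the plan's figures.** For the rule of rejecting when at least r tubes are correct, alpha = P(X ≥ r) with X ~ Bin(68, 0.91), and power = P(X ≥ r) with X ~ Bin(68, 0.98).

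| r | alpha | power |
|---|---|---|
| 65 | 0.1287 | 0.952 |
| 66 | 0.0492 | 0.845 |
| 67 | 0.0127 | 0.604 |

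Only r = 66 gives 0.0492, and its power agrees with the stated 0.84. The sample size is therefore right, and it implies exactly one rejection rule: 66 or more of 68 (97.1%).

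**Step 2. Look for that rule in the documents.** Sample Size names the test as the justification for n. Statistical Analysis names a descriptive summary. Interim Analysis lists the percentage and adverse events. Study Duration gives the enrolment target. None states the cutoff, a final test or a confidence interval.

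**Step 3. What each result would mean.** The null corresponds to 0.91 × 68 = 61.88 patients, so 62 is the first count above 91%. The one-sided p is P(X ≥ x) under p0 = 0.91. The lower limit is the exact (Clopper-Pearson) one-sided 95% limit, Beta quantile 0.05 with parameters x and 68 − x + 1.

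| Correct of 68 | % | One-sided p | Lower limit | Rejects 91%? |
|---|---|---|---|---|
| 62 | 91.2 | 0.586 | 83.3% | no |
| 63 | 92.6 | 0.418 | 85.2% | no |
| 64 | 94.1 | 0.256 | 87.0% | no |
| 65 | 95.6 | 0.129 | 89.0% | no |
| 66 | 97.1 | 0.0492 | 91.03% | yes |
| 67 | 98.5 | 0.0127 | 93.2% | yes |
| 68 | 100 | 0.0016 | 95.7% | yes |

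At 65 of 68 the two-sided 90% exact interval is 89.0% to 98.8%, which includes both 91% and 98%.

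**Step 4. How often the two readings differ.** They differ when the count is 62 to 65.

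- True rate 91%: P(X ≥ 62) − P(X ≥ 66) = 0.5862 − 0.0492 = 0.537.
- True rate 98%: 0.9996 − 0.8446 = 0.155.

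If success were read from the percentage simply exceeding 91%, the false-positive probability at the null would be 0.586 instead of 0.049.

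**Step 5. If the analysed number is not 68.** This is a contingency only, since Study Duration aims for 68 evaluable patients. With 67, a count of 65 (97.0%) has p = 0.0527 and lower limit 90.9%, so it does not reject. The cutoff becomes 66 of 67, with alpha 0.0137 and power 0.612. One patient fewer changes the operating characteristics sharply, so the rule should say how the cutoff is set for another n.

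**The case against.** The strongest reply is that the test is already specified in all but name. The null, alternative, side, test, n and significance level stand directly above the Statistical Analysis paragraph, and together they fix a single cutoff. An attained level of 0.0492 suggests that its author had a specific rejection region in view. The word introducing the list in Statistical Analysis does not rule out further analyses, and any reader given a count out of 68 can compute the p-value. On this view the gap is one linking sentence.

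Much of that stands. The documents do not contradict themselves, the intent can be inferred, and the choice of test is not wide open. What does not follow is that the test will be run: the sample-size sentence justifies n, and a cutoff that can be derived is not one that has been committed to.

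Two smaller points. First, the null is described as approximate, and Background gives malposition of 9 to 16%, that is 84% to 91% correct. At 65 of 68 the one-sided p is 0.129 against 91%, 0.082 against 90% and 0.003 against 84%. The p-values above therefore depend on the null, but 91% is the value the protocol chose, and reporting an interval lets readers judge other values. Second, a nominal ceiling of 0.05 is not in the documents, which give only 0.0492. Either ceiling gives the same cutoff at 68 (66) and at 67 (66).

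**Conclusion.** The concern holds. The sample-size arithmetic is correct, but the trial's only stated hypothesis has no committed final analysis: no test, interval or threshold. Followed as written, the plan yields a percentage that does not carry the stated alpha of 0.0492. The results affected are 62 to 65 correct of 68, where the percentage is above 91% and the null is not rejected. Such results have probability 0.537 if the true rate is 91% and 0.155 if it is 98%. This assumes 68 analysed patients, independent outcomes and the protocol's own 91% null. It should be fixed, but it does not call the design or the sample size into question.

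**What to change.** Add to Statistical Analysis:

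> The primary outcome will be tested with the exact one-sided binomial test of H0: p ≤ 0.91. With 68 evaluable patients, H0 is rejected if 66 or more tubes are correctly positioned (exact alpha 0.0492, power 0.845 at 98%). The percentage will be reported with the matching exact one-sided 95% lower limit (the lower end of the two-sided 90% interval). If the analysed number is not 68, the critical count is the smallest with exact one-sided alpha ≤ 0.05 (for example, 66 of 67).

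The 0.05 ceiling is an assumption, to be confirmed by the sponsor. The descriptive summaries already planned stay as they are.

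The cost is a few lines of text, with no extra patients or data. The one drawback for the sponsor is that results of 62 to 65 of 68 will read less favourably than the percentage alone.

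### Does closing enrolment at 68 evaluable patients with complete data let failed gauge uses drop out of the primary percentage?

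*Combined protocol and SAP*

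**What the plan says.** Study Duration sets the end of recruitment: "We plan to terminate the study after 68 evaluable patients with complete data are enrolled, per the above sample size calculation". The sample size section bases the 68 on a one-sided binomial test of 91% against 98%, "having a power of 0.84 and a significance level of 0.0492".

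The Primary Outcome is "The percentage of correct ETT position as confirmed by chest radiographs after using the NEMO™ Gauge". Study Procedure classes a tube as malpositioned if it is under 2 cm or over 5 cm from the main carina, or "in the right main stem bronchus, or in the left main stem bronchus". Statistical Analysis calls the analysis simple and descriptive, and names no analysis set or missing-data rule.

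Data Collected opens with "The following data variables will be collected for every subject" and gives a long list, from height and weight to "CXR findings and recording of distance from distal ETT to the main carina". It does not say which items make a record complete. Human Subjects/Consent explains that consent is sought before the need for intubation is known, so "we anticipate that only a portion of consented patients may ultimately have study procedures performed on them". The interim analysis is placed "at one-half enrollment (34 out of total 68 subjects"), without repeating either qualifier.

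**The concern.** Leaving out consented patients who never have the procedure is harmless. The second qualifier is the worry. Whether data are complete can be judged only after the gauge has been used, and perhaps after the film has been read, in a single-arm trial whose operator knows what was done. Read strictly, any missing item on the list could make a patient incomplete. A main-stem tube with no recorded distance to the carina could then fall out although it is plainly a failure. An attempt broken off because of apparent tissue damage, which Potential Risks foresees, has no stated place in the percentage.

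The implied success rule tolerates only two failures in 68, so a single omitted malposition could matter. The percentage would also be compared with a 91% benchmark while its own denominator was uncertain.

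**Working it through.** **1. The plan's own figure.** Inputs from the sample size section: N = 68, null rate 0.91, alternative 0.98, one-sided exact binomial test.

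- P(X ≥ 66 | 68, 0.91) = 0.0492, and P(X ≥ 66 | 68, 0.98) = 0.8446.
- One step lower, P(X ≥ 65 | 68, 0.91) = 0.1287, which exceeds 0.05.

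The stated 0.0492 and 0.84 are reproduced. They imply success at 66 or more correct of 68, a rule the plan does not write out.

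**2. What selective loss would do.** Let f be the share of attempts left out and replaced, and q the correct-position rate among them. Neither is in the documents; both are assumed. With a true rate of 0.91 over all attempts, the rate among those kept is

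r = (0.91 − f·q) / (1 − f),

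and the false-positive rate is P(X ≥ 66 | 68, r). The share of all malpositions that must be lost is f(1 − q)/0.09. Each cell gives the values at f = 1% and f = 4%.

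| q (assumed) | r | Bias, points | False-positive rate | Malpositions lost |
|---|---|---|---|---|
| 0.91 | 0.9100, 0.9100 | 0, 0 | 0.0492, 0.0492 | 1%, 4% |
| 0.80 | 0.9111, 0.9146 | 0.11, 0.46 | 0.0522, 0.0628 | 2%, 9% |
| 0.50 | 0.9141, 0.9271 | 0.41, 1.71 | 0.0614, 0.1187 | 6%, 22% |
| 0 | 0.9192, 0.9479 | 0.92, 3.79 | 0.0798, 0.3057 | 11%, 44% |

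Example: f = 0.04 and q = 0.80 give r = (0.91 − 0.032)/0.96 = 0.9146.

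Bias arises only if q is below 0.91. A record dropped for a missing height or order time, which has no evident link to tube position, belongs in the first row. Even the strict reading then costs a few extra patients and no bias: 68/(1 − f) is 68.7 at 1% and 70.8 at 4%, within the accrual of about 72 projected in Study Duration.

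**3. How fragile the result is to one omitted failure.** One-sided p-values against 0.91:

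- 66/68 gives 0.0492; adding one failure, 66/69 gives 0.122.
- 67/68 gives 0.0127; adding one failure, 67/69 gives 0.046.

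One omitted malposition therefore crosses 0.05 only from exactly 66/68. That result has probability 0.24 at a true 98% and 0.037 at 91%.

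**4. What the text supports.**

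- The Study Duration sentence governs when recruitment stops. No section says that a use with a readable film is removed from the percentage. A trial can stop at 68 complete patients and still analyse every scored use.
- The sentence ties its count to the sample size calculation, which needs one correct-or-incorrect result per patient.
- Patients consented before intubation may later prove ineligible on tube size or on oxygen saturation after intubation, or may never be intubated. That gives evaluable an ordinary meaning.
- Data Collected lists the radiograph findings as well as the distance, and main-stem placement is malposition by location. Such a tube can be scored without a distance.
- Under Study Procedure a malpositioned tube is readjusted and the distance moved is recorded. Failures therefore leave more trace in the record than successes do.
- The film follows gauge use immediately, so few missing outcomes are to be expected.

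**The case for a change.** The strongest reply is that if exclusion applied only to patients who never had the procedure, the words about complete data would add nothing. A denominator settled after results are visible in an unblinded single-arm study deserves to be fixed in advance. The projected accrual of 72 exceeds the target by four. If four attempts were left out and 66 of 68 were correct, the all-attempts result could lie anywhere from 66/72 = 91.7% (p = 0.53) to 70/72 = 97.2% (p = 0.037). A definition and a count of attempts would cost almost nothing.

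Part of this stands. The terms are undefined in the available text (the study-procedure and consent figures are not shown), and the placing of a broken-off attempt is open. The extra words still have a use on the natural reading: they require the radiograph result to be in hand. The four is recruitment headroom in the projection, not a forecast of lost films.

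The obvious alternative, counting every attempt with a classifiable film, still omits attempts without one. It would give nearly the same percentage as the natural reading, differing only for uncompleted uses. Scoring all unscored attempts as failures is a worst-case convention that the plan is not wrong to omit. Complications are already to be recorded, and adverse events go into the interim results.

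**Conclusion.** The concern does not call for a change. The wording leaves two terms undefined, but the primary outcome and the sample size calculation both point to one sensible meaning: the radiograph after gauge use can be classified. On that meaning the percentage is sound and the 0.0492 and 0.84 stand.

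The possible harm is conditional. It needs attempts to be dropped, which the text does not say, and those attempts to be correct less often than the rest, for which the documents give no evidence. With 1% to 4% lost and 80% of those correct, the bias is 0.1 to 0.5 points and the false-positive rate 0.052 to 0.063. The larger figures, up to 3.8 points and 0.306, suppose that as many as 44% of all malpositions vanish. All of these rest on assumed f and q, and on a 66-of-68 rule that is only implied by an analysis described as descriptive.

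The conclusion rests on missing films being few and not concentrated among malpositions. If the trial's results showed many attempts without a scored film, the reported percentage would need to be read with that in mind.
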